4.2.6.2 Time to first increase in OCS dose

Time from achieving the final OCS dose during the reduction phase to first asthma-related OCS increase and to first maintenance OCS dose increase during the maintenance phase will be summarised, if calculable, using median, 25th and 75th percentiles with 95% CIs calculated using complementary log-log transformation and displayed graphically using a Kaplan-Meier plot. All patients who enter the OCS reduction phase (and so have a final dose in the OCS reduction phase) will be included. Besides these cumulative statistics, the number of patients with an event and the number of patients censored will be summarised at 8 week

intervals along with the probability (and 95% CI) of no increase (Kaplan-Meier statistics) at each 8 week timepoint. This analysis will be repeated for patients who achieve 0 mg final OCS dose in reduction phase, and patients who achieve >0%, >=50%, >=75%, and >=90% OCS dose reduction in the reduction phase. For both types of time to first OCS dose increase, the number and percentage of patients with events will be summarised by the reason for the increase.

A Cox proportional hazard model will also be used to analyse time from achieving the final OCS dose during the reduction phase to the two types of first OCS increase during the maintenance phase defined in section 3.2.2; covariates will include baseline OCS daily dose and baseline categories of blood eosinophil count. If a patient withdraws from the study before increasing OCS dose or does not increase their OCS dose before the end of the maintenance phase, the time will be censored at the time of withdrawal / end of maintenance phase as applicable. The assumption of proportional hazards will be tested for covariates and appropriate action taken if the assumption is not met. The adjusted median time to the two types of 1st OCS dose increase, with 95% CI, will be reported, if calculable.

The number of patients whose OCS dose is not increased and the number of patients whose OCS dose is increased due to asthma exacerbation or worsening within 6 months during the maintenance phase will be presented. Proportions will be reported along with their estimates, and two-sided 95% confidence interval, calculated using the Kaplan-Meier time to event analysis (with 95% CI based on Greenwood's method). The number of patients with and without maintenance OCS dose increase within 6 months will be analysed in the same way. For both summaries, patients censored at the 6 month point will be summarised as still on study / in follow-up; completed study prior to 6 months; or withdrawn from study prior to 6 months.

4.2.6.3 ACQ-6

ACQ-6 scores and change from baseline ACQ-6 score will be summarised using descriptive statistics at baseline (Visit 2) (for absolute ACQ-6 scores only), Visit 3, initial morning cortisol test (time point at which OCS dose equals 5mg for 4 weeks), end of OCS reduction phase, and every 4 weeks from end of OCS reduction phase to end of maintenance phase (EOT visit) (See section 3.2.3 for windowing at these time points). Change in ACQ-6 scores at the end of maintenance phase from the end of OCS reduction phase will be summarised in the same way.

Change from baseline in ACQ-6 score at Visit 3, initial morning cortisol test, end of OCS reduction phase and end of maintenance phase will be analysed separately using an analysis of covariance (ANCOVA) with change from baseline in ACQ-6 score as the response variable, and baseline ACQ-6 score, baseline OCS dose, and baseline categories of blood eosinophil count as covariates. Adjusted means will be calculated from the ANCOVA using the observed margins approach, in which the contribution of model factors to the estimate is

weighted proportionally to the presence of these factors in the data. Results will be presented in terms of least square mean with 95% CI of change from Visit 2 in ACQ-6 score.

The number and percentage of patients who achieve improvements, no change, or deterioration, and the number and percentage of patients who achieve ACQ-6 scores of ≤ 0.75 (well controlled), >0.75 to <1.5 (partially controlled), or ≥ 1.5 (not well controlled) will be summarised. Patients with missing or non-evaluable ACQ-6 scores will be classified as “Missing”. Clopper-Pearson 95% CIs will be presented. The number and percentage of patients who achieve improvements, no change, or deterioration at the end of maintenance phase timepoint relative to the end of OCS reduction phase will also be summarised. A sensitivity analysis will be performed using a hybrid last-observation-carried-forward approach. For this analysis, patients who complete the study visit and have missing ACQ-6 scores at the visit (end of OCS reduction phase or end of maintenance phase) will have their last non-missing score carried forward. For the end of OCS reduction phase visit, this non-missing score must be on or after the date at which the patient reaches their final OCS dose of the reduction phase; for the end of maintenance phase visit, it must be during the maintenance phase. If a patient terminates early prior to the visit (end of OCS reduction phase or end of maintenance phase), the ACQ-6 score will not be imputed for that visit. Three imputation methods will be used: imputation of end of OCS reduction phase only, imputation of end of maintenance phase only, and imputation of both visits.

Shift from baseline to each of the post-baseline timepoints analysed above (i.e. Visit 3, initial morning cortisol test, end of OCS reduction phase and end of maintenance phase) and shift from end of OCS reduction phase to end of maintenance phase in asthma control status will be summarised. It will also be summarised by baseline OCS dose group defined in section 4.1.

Additionally, asthma control responders defined in section 3.2.3 will be summarised in count and proportion with 95% CIs estimated using the Clopper-Pearson method.

A sensitivity analysis will be performed using a hybrid last-observation-carried-forward approach. For this analysis, patients who complete the study visit and have missing ACQ-6 scores at the visit will have their last non-missing score carried forward. Patients who terminate early prior to the study visit will be treated as non-responders.

4.2.6.4 SGRQ

Summary statistics for SGRQ total score and component scores (symptoms, activity, and impacts) at Visit 2 (baseline) and EOT visit along with change from baseline to EOT visit will be produced. Change from baseline in SGRQ total score and the three component scores will also be analysed separately using an ANCOVA with change from baseline in SGRQ score as response variable and baseline SGRQ score and baseline OCS dose and baseline categories of blood eosinophil count as covariates. Adjusted means will be calculated from the ANCOVA using the observed margins approach, in which the contribution of model factors to the estimate is weighted proportionally to the presence of these factors in the data. Results will be presented in terms of least square mean with 95% CI of change from baseline in SGRQ total

score. Subgroup analyses (see section 4.2.5) will only include the SGRQ total score (not component scores).

In addition, SGRQ responders defined in section 3.2.4 will be summarised in count and proportion with 95% CIs estimated using the Clopper-Pearson method. No subgroup analyses will be carried out.

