2.1.2 Full analysis set

All enrolled patients who received at least one dose of benralizumab will be included in the FAS, irrespective of their protocol adherence and continued participation in the study. Patients will be analysed irrespective of whether they prematurely discontinue, according to the intent-to-treat principle. Patients who withdraw from the study will be included up to the date of their study termination.

All efficacy and safety analyses will be performed using the FAS. For consistency, demographic and baseline characteristics will be presented using the FAS.

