3.2 Secondary outcome variables

3.2.1 Change in daily OCS dose in maintenance phase

The final OCS dose in the maintenance phase should not be associated with an asthma exacerbation or adverse event. If the OCS dose recorded at the EOT/IPD visit is to treat an asthma exacerbation or AE (therapy reasons including but not limited to “Asthma exacerbation per protocol”, “Non-asthma condition”, “Adverse Event”), the final OCS dose will be defined as the last maintenance dose prior. If a patient shows asthma worsening at the EOT/IPD visit (therapy reasons “Worsening of asthma, without exacerbation”, “ACQ-6”), the final OCS dose in the maintenance phase will be the OCS dose prescribed for the worsening. If a patient withdraws during the OCS reduction phase, the final OCS dose in maintenance phase will be missing.

In order to study whether benralizumab benefits are maintained after OCS down titration or withdrawal, the absolute change in daily OCS dose from the end of the OCS reduction phase to the end of the maintenance phase (at EOT visit or IPD visit in maintenance phase) will be a secondary outcome variable calculated as follows:

$$\text{Absolute change at EOT/IPD} = \text{final OCS dose at EOT/IPD visit in maintenance phase} - \text{final dose of the OCS reduction phase}$$

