The outcome variables for ACQ-6 will be ACQ-6 scores at baseline (Visit 2), Visit 3, initial morning cortisol test, end of OCS reduction phase, and every 4 weeks from end of OCS reduction phase to end of maintenance phase (EOT visit); change from baseline in ACQ-6 score to Visit 3, initial morning cortisol test, end of OCS reduction phase, and end of maintenance phase (EOT visit); and change from the end of OCS reduction phase in ACQ-6 score to end of maintenance phase. ACQ-6, change from baseline, and change from the end of OCS reduction phase in ACQ-6 scores will also be assessed following any IPD visit. As the ACQ-6 is recorded weekly from Visit 2 to EOT, recorded scores may not coincide exactly with Visit 3 date, initial morning cortisol test, end of OCS reduction phase or EOT. For each of these timepoints, the ACQ-6 score recorded during the week (± 2 days) prior to the timepoint will be used for the outcome variable. The timing for the 4-weekly outcome variables (from the end of OCS reduction score to EOT) will be relative to the end of OCS reduction measurement, as per each patient's individual schedule. There will be no imputation for missing values.

Asthma control responder status will be evaluated as a supportive analysis. Patients will be categorized according to the following limits (Juniper et al 2005), where observed study time points include Visit 3, initial morning cortisol test (time point at which OCS dose equals 5 mg for 4 weeks), end of OCS reduction phase and end of maintenance phase (EOT visit):

- Improvement: Change from baseline in ACQ-6 score of ≤ -0.5
- No change: Change from baseline in ACQ-6 score of > -0.5 and $< +0.5$
- Deterioration: Change from baseline in ACQ-6 score of $\geq +0.5$

Asthma control responders will be defined as patients who had improvements based on the change from baseline in their ACQ-6 scores. Patients with no change or deterioration according to ACQ-6 score evaluation will be defined as non-responders. Patients with missing or non-evaluable ACQ-6 scores at a post-baseline assessment time point will be considered non-responders at the time point. (Note that baseline will be as defined in section 2.3 and will not be imputed (if missing) as for safety monitoring.)

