3.2.4 St. George's Respiratory Questionnaire (SGRQ)

The change from baseline (Visit 2) in SGRQ total scores to the end of maintenance phase (EOT) is a secondary endpoint of this study. The SGRQ will be completed on site at the beginning of Visit 2 and EOT/IPD visit using the ePRO device.

The SGRQ is a 50-item PRO instrument developed to measure the health status of subjects with airway obstruction diseases (Jones et al 1991). The questionnaire is divided into 2 parts:

- Part 1 consists of 8 items that pertain to the severity of respiratory symptoms in the preceding 4 weeks;
- Part 2 consists of 42 items related to the daily activity and psychosocial impacts of the individual's respiratory condition.

The SGRQ yields a total score and 3 component scores (symptoms, activity, and impacts). The total score indicates the impact of disease on overall health status. This total score is expressed as a percentage of overall impairment, in which 100 represents the worst possible health status and 0 indicates the best possible health status. Likewise, the component scores range from 0 to 100, with higher scores indicative of greater impairment. Specific details on the scoring algorithms are provided by the developer in a user manual (Jones et al 2009).

A 4-point threshold will be used to define a response in SGRQ. If there is a ≥ 4 -point decrease from baseline in SGRQ total score, it will be defined as 'improvement'; if there is a ≥ 4 -point increase at EOT from baseline, it will be defined as 'worsening'; if the absolute change is less than 4 points at EOT, it will be defined as 'no change'. Response will also be assessed following any IPD.

The symptoms component score will be set to missing if there are >2 missing items; activity component score will be set to missing if there are >4 missing items; impacts component score will be set to missing if there are >6 missing items; and total score will be set to missing if one of the 3 component scores is missing.

To avoid incorrectly setting component and/or total scores to missing when items are logically skipped, the following items should **not** be considered as missing if logically skipped in the context of the subject's prior responses:

Question 6 (Length of worst attack of chest trouble):

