6. CHANGES OF ANALYSIS FROM PROTOCOL

- 1) A sensitivity analysis of the primary outcome has been included in section 4.2.5.2 which excludes any patients with an Important Protocol Deviation related to efficacy. This sensitivity analysis is not specified in the protocol.
- 2) A sensitivity analysis of the first key supportive analysis has been included in section 4.2.5.2 which will require patients with a baseline daily OCS dose of 5mg to achieve a final daily OCS dose of < 5 mg, unless the reason for no further reduction is complete AI. This sensitivity analysis was not included in the protocol.
- 3) In protocol Section 8.5.2.2, a mixed model for repeated measures was planned to analyse the change from baseline in ACQ-6 score. Because phase and study duration will be different between patients, an ANCOVA model will be used to analyse the change from baseline at visit 3, initial morning cortisol test, end of OCS reduction phase and end of maintenance phase, only.

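### Mean SGRQ change is analysed at EOT only, and the IPD assessment provided for ACQ-6 change has no method, so early stoppers are absent from both end-of-maintenance means

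*SAP*

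**What the plan says.** **SGRQ.** SAP 3.2.4 fixes the endpoint: "The change from baseline (Visit 2) in SGRQ total scores to the end of maintenance phase (EOT) is a secondary endpoint of this study". It also fixes the collection: "The SGRQ will be completed on site at the beginning of Visit 2 and EOT/IPD visit using the ePRO device". IPD enters the definitions once more, for the response category: "Response will also be assessed following any IPD". In the methods, SAP 4.2.6.4 says that summary statistics for the total and component scores "at Visit 2 (baseline) and EOT visit along with change from baseline to EOT visit will be produced". The ANCOVA that follows names no visit of its own. SAP 2.4 leaves missing data unimputed unless stated otherwise.

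**ACQ-6.** SAP 3.2.3 says that changes, both from baseline and from the end of OCS reduction, "in ACQ-6 scores will also be assessed following any IPD visit". SAP 4.2.6.3 lists its summary and ANCOVA time points without an IPD entry. SAP section 6 limits the ANCOVA to Visit 3, the initial morning cortisol test, "end of OCS reduction phase and end of maintenance phase, only".

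**OCS dose.** SAP 3.2.1 takes the final dose "at EOT visit or IPD visit in maintenance phase". Patients who withdraw in the reduction phase have a missing value. SAP 4.2.6.1 then repeats the summary without patients who withdraw before EOT.

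**Analysis set.** SAP 2.1.2 states: "Patients will be analysed irrespective of whether they prematurely discontinue, according to the intent-to-treat principle".

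**The concern.** The SGRQ has one scheduled post-baseline measurement per patient: at EOT for those who finish and at IPD for those who stop. A mean defined at EOT only therefore discards the one follow-up score that a discontinuing patient provides. It is a mean among completers, reported under an analysis set that includes everyone dosed. For ACQ-6 the definitions section provides for an IPD assessment, but the methods section does not say how it will be shown.

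This matters because stopping can be related to outcome. Protocol 3.6 lists adverse events and an asthma event needing mechanical ventilation among the reasons for stopping study drug. If such patients have worse scores, mean quality of life and asthma control after down-titration will look better than they were among all treated patients. The mean and the responder proportion for SGRQ will also describe different patients: a patient whose change cannot be evaluated counts as a non-responder but is simply absent from the mean.

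**Working it through.** **1. Is there a figure in the plan to reproduce?** Not on this point. The only precision figure is in SAP 1.3: a 95% interval extending about 4.1 points from 50% with 600 patients. Exact Clopper-Pearson limits for 300/600 give ±4.08, which agrees. That figure concerns the primary proportion and has no bearing here.

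**2. Follow an early stopper through the SGRQ rules.**
- Protocol 3.6.1 and Table 1: the patient attends an IPD visit, where the SGRQ is completed. The later follow-up contact has no SGRQ.
- SAP 3.2.4: the IPD score can give a response category.
- SAP 4.2.6.4: the summary uses Visit 2 and EOT. The ANCOVA response is change from baseline, which by the endpoint definition means change to EOT.
- SAP 2.4: nothing fills the empty EOT value.
- Result: no contribution to the mean or the ANCOVA, although a measured score exists.

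**3. Follow the same patient through the ACQ-6 rules.**
- Weekly scores feed the summaries at Visit 3, the cortisol test, the end of reduction and every 4 weeks after that, up to the point of stopping.
- SAP 3.2.3 promises change at IPD, but 4.2.6.3 has no table or model for it.
- In the carry-forward analysis of change categories, a patient who terminates before the visit is not imputed. In the responder version that patient is a non-responder.
- Protocol 8.5.2.2 planned a mixed model for repeated measures, which would have used such a patient's earlier scores. SAP section 6 replaces it with separate ANCOVAs because phase lengths differ, and does not mention this consequence.
- Result: absent from the end-of-maintenance ANCOVA.

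**4. Compare with OCS dose.** There the main summary includes IPD visits in the maintenance phase, and a second summary excludes early withdrawals, so both views are shown. For mean SGRQ and ACQ-6 change at the end of maintenance, only the EOT view has a method.

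**5. Size.** Let d be the share with no EOT score and D the amount by which their mean change is worse. The mean over everyone is (1 − d) × (EOT mean) + d × (mean of the others), so the EOT mean is too favourable by d × D. The documents give neither d nor D, and no mean or SD for either score. All values below are assumed.

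| d | Patients of 600 | SGRQ, D = 5 | SGRQ, D = 15 | ACQ-6, D = 0.5 | ACQ-6, D = 1.0 |
|---|---|---|---|---|---|
| 5% | 30 | 0.25 | 0.75 | 0.025 | 0.05 |
| 10% | 60 | 0.50 | 1.50 | 0.05 | 0.10 |
| 15% | 90 | 0.75 | 2.25 | 0.075 | 0.15 |

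The reference values in the SAP are 4 points for SGRQ and 0.5 for ACQ-6. Every entry lies below them.

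**6. What IPD scores can recover.** Let e be the share with an EOT score, and m the share with a maintenance-phase IPD score and no EOT score. Adding the latter moves the mean by m/(e + m) × D, with D now taken for that group. Patients who stopped earlier or were lost to follow-up are not recovered.

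**The case against.** The strongest reply is that the SAP follows the protocol. Protocol 2.2, 8.4 and 8.5.2.3 all define SGRQ change to the end of maintenance at EOT, and Protocol 8.4 rules out imputation for continuous scores while counting withdrawals as failures for response outcomes. The difference between mean and responder results is therefore a stated rule, not an oversight. An IPD visit falls about 4 weeks after the last dose at whatever stage the patient stopped, possibly before any OCS reduction. Pooling such a score with an end-of-maintenance score answers a different question. This stands, and it is why EOT should remain the main analysis. It does not argue against a labelled second analysis: using a measured IPD score is not imputation.

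A reader might infer that ACQ-6 is also confined to EOT, or that early stoppers vanish from SGRQ and ACQ-6 altogether. The documents do not support either. SAP 3.2.3 provides for change at IPD, the 4-weekly summaries use scores up to stopping, and SGRQ response covers IPD and counts a non-evaluable change as non-response. For ACQ-6 the fault is a provision not carried into the methods.

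A reader might also take SAP 3.2.1 as a precedent for using any IPD visit. It covers only those in the maintenance phase.

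Finally, not every stopper need do worse. Protocol 3.6 also lists patient decision, pregnancy and eligibility findings. This stands too: the direction is likely but not established.

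**Conclusion.** The point holds for two specific results: mean SGRQ change (summary and ANCOVA) and the end-of-maintenance ACQ-6 ANCOVA. Patients who discontinue are absent from both. For SGRQ this is because the method stops at EOT although IPD scores are collected. For ACQ-6 it is because the IPD assessment in 3.2.3 has no method in 4.2.6.3 or section 6.

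It would go too far to call this a breach of the intent-to-treat principle. SAP 2.1.2 defines who belongs to the full analysis set and includes withdrawn patients up to the date they leave the study; it does not promise an end-of-maintenance value for each of them.

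The size is unknown. With 5–15% stopping early and 5–15 points worse, both assumed, the SGRQ mean is too favourable by 0.25 to 2.25 points. That range also assumes that those without an EOT score do worse on average. These are secondary, descriptive endpoints in a single-arm study, so no hypothesis test, sample size or primary result depends on them. The addition is worth making because it is cheap and shows whether the means depend on who is left out.

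**What to change.** Keep the EOT analyses in SAP 4.2.6.3 and 4.2.6.4 as the main ones. In each section add:

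- A sensitivity summary and ANCOVA, labelled as such, of change from baseline to EOT or, where there is no EOT score, to an IPD visit in the maintenance phase. This matches the visit rule in 3.2.1. Use the same covariates, and show the result beside the EOT result with the number of patients in each.
- A separate descriptive display of scores from IPD visits in the reduction phase or earlier, not pooled with the above.
- For ACQ-6, a sentence saying that this is how the IPD assessment in 3.2.3 is reported.

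The cost is one further run of existing programs on data already collected. There are two drawbacks to state with the result: IPD scores come at varying times on treatment, and patients lost to follow-up remain missing, so only part of the gap is closed.
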